## 2.2 Treatments, Study Groups and Treatment Assignment

Patients will be randomly allocated to either receive *MC2-25 cream*, white oil-in-water, topical emulsion containing the active ingredient, Alanyl-Glutamine (Ala-Gln) in the aqueous phase at a concentration of 30 mg/g or *MC2-25 vehicle*, which is identical to *MC2-25 cream* without the active ingredient.

*MC2-25 cream*, or *MC2-25 vehicle*, must be applied by the patient after each toilet visit following urination (during day and night) starting on the day of the Baseline visit. Assuming, a maximum of 12 toilet visits are needed over a period of 24 hours and a maximum of 0.5 g cream per application, the maximum daily dose is expected to be around 6.0 g.

The sponsor, sponsor representatives, and all patients, monitors, and site staff will be blinded throughout the trial. Instructions for emergency unblinding are provided in CTP Section 10.2.1. The staff at the investigational medicinal product (IMP) manufacturing site and the external statistician responsible for preparing the randomisation list are not blinded.

Each patient will be assigned a unique randomisation number determining which study treatment the patient will receive. These randomisation numbers will be based on a supply list accompanying the IMP provided to the sites and the same randomisation number named as kit no. will also be listed on the applicable IMP. At each dispense, this kit no. will be documented in the eCRF linking the IMP to the correct patient. No patient ID, other than the kit no. will be written on the IMP.

## 2.3 Study Objectives

### 2.3.1 Primary Objectives

To explore the efficacy of *MC2-25 cream* compared to *MC2-25 vehicle* in vulvar lichen sclerosus (VLS).

### 2.3.2 Secondary Objectives

- To explore the safety of *MC2-25 cream* compared to *MC2-25 vehicle* in VLS.
- To explore the burden of VLS on women's lives.

## 2.4 Study Endpoints

### 2.4.1 Efficacy

The primary endpoint is the mean change in weekly mean Worst Itch Numeric Rating Score (WI-NRS) recorded in the patient's diary from Baseline to Week 12 for *MC2-25 cream* compared to *MC2-25 vehicle*.

(Weekly mean WI-NRS is calculated as the average of WI-NRS values recorded in the patient's diary for 7 days prior to the in-clinic visits).

The secondary endpoints (all defined from Baseline to Week 12 for MC2-25 cream compared to MC2-25 vehicle) are:

- Mean change in weekly mean Worst Pain Numeric Rating Score (WP-NRS) recorded in the patient's diary (Weekly mean WP-NRS is calculated as the average of WP-NRS values recorded in the patient's diary for 7 days prior to the in-clinic visits.)
- Percentage of patients obtaining a  $\geq 4$ -point improvement in weekly mean WI-NRS recorded in the patient's diary
- Percentage of patients obtaining a  $\geq 4$ -point improvement in weekly mean WP-NRS recorded in the patient's diary
- Percentage of patients obtaining a  $\geq 3$ -point improvement in weekly mean WI-NRS recorded in the patient's diary
- Percentage of patients obtaining a  $\geq 3$ -point improvement in weekly mean WP-NRS recorded in the patient's diary
- Change in Skindex-29 domains

Primary and secondary endpoints will be confirmatorily analyzed as described in Sections 5.2 to 5.5. Other endpoints will be exploratorily analyzed.

Other endpoints (all defined from Baseline to Week 12) include:

- Percentage of patients obtaining a complete response (score  $\leq 1$ ) in weekly mean WI-NRS recorded in the patient's diary
- Percentage of patients obtaining a complete response (score  $\leq 1$ ) in weekly mean WP-NRS recorded in the patient's diary
- Mean change in Worst Itch Numeric Rating Score (WI-NRS) recorded at in-clinic visits
- Mean change in Worst Pain Numeric Rating Score (WP-NRS) recorded at in-clinic visits
- Mean change in Worst Penetrative sex related Pain Numeric Rating Score (WPP-NRS) recorded at in-clinic visits
- Percentage of patients obtaining a  $\geq 3$ -point improvement in WI-NRS recorded at in-clinic visits
- Percentage of patients obtaining a  $\geq 3$ -point improvement in WP-NRS recorded at in-clinic visits
- Percentage of patients obtaining a  $\geq 3$ -point improvement in WPP-NRS recorded at in-clinic visits
- Percentage of patients who reported an improvement\* in Patient's Global Impression of Change (PGIC) for Worst Itch (WI), Worst Pain (WP) or Worst Penetrative sex related Pain (WPP)
- Percentage of patients who reported an Important improvement in Patient's Global Impression of Change (PGIC) for Worst Itch (WI), Worst Pain (WP) or Worst Penetrative sex related Pain (WPP)
- Mean change in VQLI total score
- Mean change in Vulvar lichen sclerosus Area and Sign Severity Index (VASSI)
- Mean change in VASSI Area scores
- Mean change in VASSI Sign scores
- Mean change in Clinician's Global Assessment (CGA) of VLS
- Percentage of patients with a  $\geq 2$ -point improvement in Clinician's Global Assessment (CGA) of VLS
- Percentage of patients with an improvement\* in the Clinician's Global Impression of Change (CGIC) assessment
- Burden of VLS on women's lives as reported on the "VLS patient journey sheet"

Note: \* Improvement = 'Very much better', 'Much better' or 'A little better'

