VLS prevalence increases with age as described in Section 2.2.1. Consequently, a considerable amount of elderly (>65 years of age) patients is expected to be enrolled. Elderly patients are considered a vulnerable population due to potential comorbidities and polypharmacy but not due to their VLS. In view of the favourable systemic and local safety profiles described above, there are no specific eligibility criteria for elderly patients. Likewise, there are no specific safety surveillance measures during the trial for elderly patients. Exclusion criterion 6, Section 5.2 ‘Any chronic or acute medical condition that, in the opinion of the investigator, may pose a risk to the safety of the patient or may interfere with the assessment of efficacy in this trial’ will ensure that elderly patients are not enrolled in the trial if they have significant comorbidities.

In view of the major impact of VLS on patient’s quality of life, the potential benefits of MC2-25 cream on VLS, and the benign safety profile of MC2-25 cream, the benefit-risk ratio for the current trial is considered positive. In view of the benign nature of the potential risks a Data Safety Monitoring Board is not considered necessary.

3 Objectives and endpoints

Primary objective:

To explore the efficacy of MC2-25 cream compared to MC2-25 vehicle in vulvar lichen sclerosus (VLS).

Primary endpoint:

Mean change in weekly mean Worst Itch Numeric Rating Score (WI-NRS) recorded in the patient's diary from Baseline to Week 12 for MC2-25 cream compared to MC2-25 vehicle. (Weekly mean WI-NRS is calculated as the average of WI-NRS values recorded in the patient's diary for 7 days prior to the in-clinic visits).

Secondary endpoints:

- Mean change in weekly mean Worst Pain Numeric Rating Score (WP-NRS) recorded in the patient's diary from Baseline to Week 12 for MC2-25 cream compared to MC2-25 vehicle. (Weekly mean WP-NRS is calculated as the average of WP-NRS values recorded in the patient's diary for 7 days prior to the in-clinic visits.)
- Percentage of patients obtaining a ≥ 4 -point improvement in weekly mean WI-NRS recorded in the patient's diary from Baseline to Week 12 for MC2-25 cream compared to MC2-25 vehicle.
- Percentage of patients obtaining a ≥ 4 -point improvement in weekly mean WP-NRS recorded in the patient's diary from Baseline to Week 12 for MC2-25 cream compared to MC2-25 vehicle.

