9.1 Statistical hypotheses

On the primary and all secondary endpoints, treatment groups will be compared for superiority of MC2-25 cream over MC2-25 vehicle. The null hypothesis is of no difference between the two treatment groups. For further details see Section 9.4.1.

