9.4 Statistical analyses

9.4.1 General approach

The methodology presented below represents a brief overview of the statistical methods that will be fully detailed in the statistical analysis plan (SAP). The SAP will be finalised before the database is locked. Any changes to the methods described in the final SAP will be described and justified in the clinical trial report. All statistical analyses will be performed using SAS statistical software (Version 9.4 or higher).

Statistical significance will be tested at the two-sided 5% significance level unless otherwise specified. Superiority is concluded if a p-value of statistical hypothesis testing is below the significance level and the estimate of treatment difference is in favourable direction for MC2-25 cream. Estimates of treatment effects and differences at timepoints other than Week 12 will be reported exploratively.

Categorical variables will be described by summary tables of frequencies (counts and percentages) per treatment group, continuous parameters by displaying arithmetic mean, median, minimum and maximum values, standard deviation, and, where applicable, interquartile ranges.

All collected and derived data will be presented in individual patient data listings.

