9.4.5 Planned interim analyses

The current trial is a phase 2 trial and is powered to detect statistical significance on the primary endpoint and to inform further clinical development. The expected recruitment period is relatively short, and the double-blind treatment period is only 12 weeks. Thus, no interim analysis is planned.

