## 5.2 Statistical Hypotheses

Let  $\mu_M$  and  $\mu_V$  be estimators of treatment effect for each endpoint for MC2-25 cream, and MC2-25 vehicle. The following statistical hypothesis will be tested.

$$H_0: \mu_M = \mu_V \text{ versus } H_1: \mu_M \neq \mu_V$$

Statistical significance will be tested at the two-sided 5% significance level unless otherwise specified. Superiority is concluded if a p-value of statistical hypothesis testing is below the significance level and the estimate of treatment difference is in a favourable direction for MC2-25 cream. Estimates of treatment effects and differences from baseline at time points other than Week 12 will be reported exploratively.

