## 5.3 Multiplicity Adjustment and Estimands

No multiple testing adjustment will be employed in this study.

The primary endpoint will be analyzed by different estimands, following a treatment policy strategy with imputation (primary estimand) (Section 4.7.2), a treatment policy strategy without imputation (secondary estimand), and a while on treatment strategy without imputation (tertiary estimand).

For the primary estimand, all available data will be used, regardless of treatment and treatment adherence, with missing data imputed as described in Section 4.7.2. For the secondary estimand, all available data will be used, regardless of treatment and treatment adherence, and missing data will not be imputed.

For the tertiary estimand, all available data will be included up to 7 days after the last treatment intake, regardless of treatment and treatment adherence, and missing data will not be imputed. Data more than 7 days after the last treatment intake is invalid and will not be used.

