#### Mixed Model of Repeated Measures (MMRM)

Comparisons will be done using an MMRM model including treatment, visit, treatment-by-visit interaction, as factors, and menopausal status at baseline, ICIQ-UI-SF score at baseline, and the baseline value of the respective endpoint as covariates.

The statistical model is

$$\text{Endpoint} = \beta_0 + \beta_1 \text{Otreatment} + \beta_2 \text{OVisit} + \beta_3 \text{OTreatment-by-visit} + \beta_4 \text{Omenopausal status} + \beta_5 \text{OICIQ-UI-SF score} + \beta_6 \text{Obaseline value} + \text{error},$$

where  $\beta_1$  -  $\beta_6$  are parameters of fixed effects and  $\beta_0$  an intercept. The estimated treatment differences between MC2-25 cream and MC2-25 vehicle, will be reported together with the associated standard error, the 95% confidence interval, and a p-value of a test on the respective contrast corresponding to the hypothesis of no difference between treatments (superiority) (Section 5.2).

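### The primary and all secondary endpoints are called confirmatory and can each yield a superiority conclusion at 5%, with no adjustment, gate or test order

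*SAP*

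**What the plan says.** - **Status of the endpoints.** SAP 2.4.1: "Primary and secondary endpoints will be confirmatorily analyzed as described in Sections 5.2 to 5.5". The next sentence there makes the other endpoints exploratory. SAP 5.5.5 likewise describes only the other and safety endpoints as exploratory.
- **Scope of testing.** Protocol 9.1: "On the primary and all secondary endpoints, treatment groups will be compared for superiority of MC2-25 cream over MC2-25 vehicle". SAP 5.2 sets up the null hypothesis for each endpoint.
- **Decision rule.** SAP 5.2: "Superiority is concluded if a p-value of statistical hypothesis testing is below the significance level". The rule also needs a favourable direction; Protocol 9.4.1 has the same rule and requires that "the estimate of treatment difference is in favourable direction for MC2-25 cream". The level is two-sided 5% for every test. Only time points other than Week 12 are set aside as exploratory.
- **Error control.** SAP 5.3: "No multiple testing adjustment will be employed in this study".
- **Order.** SAP Table 5 has a column headed *Sequence*, but it holds only the labels Primary and Secondary. No stopping rule or condition goes with it.
- **Purpose.** The primary objective (Protocol section 3, SAP 2.3.1) is worded as exploring efficacy. Protocol 9.4.5 says the trial is "powered to detect statistical significance on the primary endpoint and to inform further clinical development".

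**The concern.** Leaving multiplicity unadjusted is usual in a phase 2 trial when the secondary endpoints are treated as exploratory. Here the SAP calls them confirmatory and attaches a formal superiority conclusion to each, while declining any control over the set. That contradicts the exploratory objective and a sample size justified for the itch score alone.

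In practice, if the primary analysis is not significant but pain, or one Skindex-29 domain, reaches p < 0.05 in the right direction, the plan as written allows the report to conclude superiority on that endpoint as a confirmatory result. Each test has its own 2.5% limit in the favourable direction, but nothing limits the error across the set. Because the trial is meant to guide further development, an isolated finding of this kind from 33 patients could be carried forward as established.

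**Working it through.** **1. The plan's own figure.** Protocol 9.2 gives at least 78% power for the primary endpoint with 16 to 17 patients per arm, an effect of 1 SD and two-sided 5%. For a two-sample t-test the noncentrality is d·√(n₁n₂/(n₁+n₂)). With 16 and 16 this is √8 = 2.83, giving 78.1%. With 16 and 17 it is √(272/33) = 2.87, giving 79.4%. The stated figure is reproduced, and it concerns the primary endpoint only. The documents give no error rate for the set of endpoints.

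**2. Number of tests under the rule.**
- Primary: change in WI-NRS, 1 test.
- Continuous secondary: change in WP-NRS (1) and the three Skindex-29 domains (3), 4 tests.
- Responder secondary: at least 3 and at least 4 points, for itch and for pain, 4 tests.

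For the five continuous tests, the MMRM part of SAP 5.4.3 names "a p-value of a test on the respective contrast corresponding to the hypothesis of no difference between treatments", so the rule plainly applies. For the four responder endpoints, SAP 5.4.1 and 5.5.2 name a log odds ratio with its confidence interval but no between-group p-value, while Protocol 9.1 still includes them in the superiority comparison. The count is therefore five or nine, depending on how that gap is read.

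**3. Exact values if the tests were independent and the cream had no effect.** Each test gives a false superiority conclusion with probability 0.025.
- Primary alone: 2.5%.
- At least one of five: 1 − 0.975⁵ = 11.9%.
- Primary not declared superior, at least one of four continuous secondaries declared superior: 0.975 × (1 − 0.975⁴) = 9.4%.

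**4. Allowing for correlation.** The documents give no correlations, so they are assumed. Null simulation, 40,000 trials per setting, 17 versus 16 patients:
- Five continuous changes with a common correlation, compared by t-tests.
- Responders derived from the same itch and pain scores (assumed SD 2.5, assumed mean change −1 or −2), compared by unadjusted Wald tests of the log odds ratio. Tables that cannot be estimated count as non-significant.

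Paired entries are for mean change −1 / −2. Monte Carlo standard error is about 0.2 percentage points or less.

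| Assumed correlation | Any false superiority, 5 tests | Any false superiority, 9 tests | Secondary claimed, primary not significant, 5 tests | Same, 9 tests |
|---|---|---|---|---|
| 0 | 12.1 / 11.8% | 13.1 / 14.7% | 9.6 / 9.3% | 10.6 / 12.3% |
| 0.5 | 9.4 / 9.3% | 10.2 / 11.7% | 6.9 / 6.7% | 7.8 / 9.1% |
| 0.7 | 7.5 / 7.3% | 8.2 / 9.8% | 5.0 / 4.9% | 5.8 / 7.4% |
| 0.9 | 5.0 / 5.2% | 5.9 / 7.6% | 2.6 / 2.7% | 3.5 / 5.0% |

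Eligibility sets a minimum for itch but none for pain, so some patients cannot reach a pain response. With baseline pain assumed uniform on 0 to 8, the nine-test figures become 12.6 / 13.8% at correlation 0, 9.9 / 11.1% at 0.5 and 5.5 / 7.0% at 0.9. The conclusion does not change.

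**5. A cruder cross-check.** Treating all nine tests as equally correlated normal statistics, each at the full 2.5%, gives 20.4% at correlation 0, 13.6% at 0.5, 10.0% at 0.7 and 6.2% at 0.9. These are mostly higher than the simulated nine-test values. The simulation derives the nested responder endpoints from the same scores as the continuous ones and counts non-estimable tables as non-significant.

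**6. With superiority reserved for the primary.** The false superiority rate is 2.5% in the favourable direction, the chance of a secondary claim after a failed primary is 0, and primary power stays at 78.1–79.4%. Bonferroni over nine tests (0.05/9 = 0.0056) would instead cut primary power to about 47% with 16 and 17 patients, so it is not what is needed here.

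**The case against.** The strongest reply is that the stakes are small. This is a 33-patient phase 2 trial with a single primary endpoint whose error rate is intact. The absence of adjustment is stated openly, so a reader can discount the secondaries, and no go/no-go rule depends on them. The word confirmatory may also mean no more than that these endpoints are modelled while the others are only tabulated. All of this bears on weight. It does not remove the superiority rule, which stands separately in SAP 5.2 and Protocol 9.1 and 9.4.1.

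The count of tests can also be questioned. SAP 5.5.2 speaks of two continuous secondary endpoints, taking Skindex-29 as one. But its three domain scores are reported separately with no combined score, so there are three comparisons and three chances of a claim. For responders, a rule that needs a p-value cannot strictly be applied where none is named. The nine-test figures also depend heavily on the assumed SD and mean change and on a test the SAP does not specify. That is fair: they are illustrative, and the five-test figures should carry the argument.

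Finally, the upper ends need uncorrelated endpoints. That is implausible, since the Skindex-29 Symptoms domain contains itch and pain items. At a correlation of 0.9 the five-test figure is only about 5%.

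**Conclusion.** The concern holds. As written, the plan lets any secondary endpoint be declared superior in a confirmatory sense whether or not the primary succeeds, which conflicts with the exploratory objective.

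If the cream has no effect, the chance of at least one false superiority conclusion over the five continuous tests is about 7–9% at correlations of 0.5 to 0.7, within a full range of 5–12%. For the primary alone it is 2.5%. A false secondary claim with a non-significant primary has a chance of about 5–7% at the same correlations, within a range of about 3–9%. If the responder endpoints are included, the ranges are about 6–15% and 3–12%.

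These sizes rest on assumed correlations and, for responders, an assumed SD and mean change. Simple t and Wald tests stand in for the planned multiple imputation with MMRM and for the covariate-adjusted logistic regression. That the plan permits such a claim follows from the text and needs none of these assumptions.

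**What to change.** Before unblinding:

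- In SAP 2.4.1, 5.2 and 5.3, name the primary analysis (FAS, treatment policy, multiple imputation) as the only confirmatory test and the only one that can yield a superiority conclusion.
- State that secondary estimates, confidence intervals and any p-values are nominal and exploratory.
- Record this in SAP 5.6 as a departure from Protocol 9.1 and 9.4.1, which would otherwise still say the opposite.
- If the sponsor wants confirmatory secondary claims, pre-specify a gate on the primary and an order among the secondaries. In that case also settle whether the responder endpoints are tested, and by which p-value.

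The cost is wording plus one SAP 5.6 entry. No patients are added, and the primary keeps its full 5% level and stated power. The one loss is that an isolated secondary p < 0.05 can no longer be reported as superiority. The documents do not show whether unblinding is still ahead: the SAP is dated 30 October 2024 and says recruitment ended at 33 patients. If it has already taken place, the same restriction on wording belongs in the clinical trial report.

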**Patient reported outcomes (PRO) assessments****Worst Itch Numeric Rating Score (WI-NRS) of VLS**

The patient's WI-NRS score must be recorded by the patient in a diary once daily (i.e., every day around the same timepoint, e.g. morning, afternoon or evening) for a total of 7 days (i.e. starting 7 days before the next in-clinic visit and ending on the day before the next in-clinic visit) leading up to each in-clinic visit day at Baseline, Week 1, Week 4, Week 8, and Week 12 or End of Treatment (EoT) using an 11-point numeric rating scale ranging from 0 to 10:

*Please score the intensity of the Worst Itch associated with your lichen sclerosus, that you have experienced in the past 24 hours: 0 (no itch), 1, 2, 3, 4, 5, 6, 7, 8, 9, 10 (worst imaginable itch).*

In addition, the patient's WI-NRS score must be reported to the clinical staff at in-clinic visits at Screening 1, Baseline, Week 1, Week 4, Week 8, and Week 12 (or EoT) using the 11-point numeric rating scale above.

**Worst Pain Numeric Rating Score (WP-NRS) of VLS**

The patient's WP-NRS score must be recorded by the patient in a diary once daily (i.e., every day around the same timepoint, e.g. morning, afternoon or evening) for a total of 7 days (i.e. starting 7 days before the next in-clinic visit and ending on the day before the next in-clinic visit) leading up to each in-clinic visit day at Baseline, Week 1, Week 4, Week 8, and Week 12 (or EoT) using an 11-point numeric rating scale ranging from 0 to 10:

*Please score the intensity of the Worst Pain\* associated with your lichen sclerosus, that you have experienced in the past 24 hours: 0 (no pain), 1, 2, 3, 4, 5, 6, 7, 8, 9, 10 (worst imaginable pain).*

\*Pain includes sensations such as Burning, Stinging, Soreness and Irritation.

In addition, the patient's WP-NRS score must be reported to the clinical staff at in-clinic visits at Screening 1, Baseline, Week 1, Week 4, Week 8, and Week 12 (or EoT) using the 11-point numeric rating scale above.

**Worst Penetrative sex related Pain Numeric Rating Score (WPP-NRS) of VLS**

At Screening 1, Baseline, Week 4, Week 8, and Week 12 (or EoT) visits all patients must indicate whether they are sexually active or not by answering Question 1 below. Patients who answer No to Question 1, must subsequently answer only Question 2. Patients who answer Yes to Question 1 must subsequently answer Questions 2, 3, and 4, and finally in Question 5 report their Worst Penetrative sex related Pain on an 11-point numeric rating scale ranging from 0 to 10 as also described below:

1. Have you had penetrative sex during the past 4 weeks? (Yes/No) If No, please answer Question 2 only. If Yes, please answer Questions 2, 3, 4 and 5.
2. Have you abstained from penetrative sex during the past 4 weeks due to your vulvar lichen sclerosus? (Yes/No)
3. How many times have you had penetrative sex during the past 4 weeks? (X times)
4. Have you used lubricants during penetrative sex during the past 4 weeks? (Yes/No)
5. Please score the intensity of the Worst Penetrative sex related Pain\* you have experienced due to your lichen sclerosus in the past 4 weeks: 0 (no penetrative sex related pain), 1, 2, 3, 4, 5, 6, 7, 8, 9, 10 (worst imaginable penetrative sex related pain).

\*Pain includes sensations such as Burning, Stinging, Soreness and Irritation.

